4.0 Test Schedule

4.1 Test schedule for metastatic CRC

Tests and procedures	Screening		Active Monitoring Phase					
	Reg	Cycle 1	Cycle 2 (2 nd dose of Durva + Y90-RE)*	Cycle 3	Cycle 4	Cycle 5	End of treatment visit ¹²	Clinical Follow-up ¹³ (every 3 months)
Window	21 days	±5 days	±5 days	±5 days	±5 days	±5 days	±5 days	
History and exam ³ , Wt ⁵ , BP, HR, ECOG PS	X							
Exam, Wt ⁵ , BP, HR, ECOG PS		X	X	X	X	X	X	X
Adverse event assessment	X	X	X	X	X	X	X	X
Concomitant medication review	X	X	X	X	X	X	X	X
Height	X							
IR Consult	X							
Pregnancy test ¹	X		X		X		X	X
Hematology group CBC w/ 5-part differential	X	X	X	X	X	X	X	X
Chemistries ²¹	X	X	X	X	X	X	X	X
Thyroid Function Test TSH, free T4, amylase, lipase, Vitamin D	X		X		X		X	X
Creatinine clearance	X	X	X	X	X	X	X	X
Coagulation PT, PTT, INR	X						X	
Cholesterol, triglycerides	X							
IR Tc-99m labelled MAA eligibility mapping		X ¹⁸						
Tumor measurement ²	X						X	X
ECG ⁶	X		X		X		X	
Urinalysis ⁷	X	X	X	X	X	X	X	X
Administer durvalumab ^{8,R}		X ^{16,17,18,19}	X ^{9,16,17,18,19}	X ¹⁹	X ^{17,18,19}	X ^{17,18,19}		
Administer Y90-RE			X					
Patient Questionnaire Booklets ⁴ (Appendix III)		X	X	X	X	X	X	
Mandatory Research Specimens (see companion Lab Manual) ^{10,R}	X	X ^{14,15,16,17}	X ^{14,15,16,17}	X ¹⁷	X ^{15,16,17}	X ^{15,16,17}	X	
Mandatory Research Tissue specimens (see companion Lab Manual) 11,R	X (Pre- treatment) ₁₈						X (Post- treatment) _{19, 20}	

Cycle = 14 days

1. For women of childbearing potential only. Serum pregnancy test. Must be done \leq 7 days prior to registration.
2. A scan is required at baseline prior to the first dose of durvalumab. The scan does not need to be repeated as long as it is \leq 28 days prior to registration. Preferably we would recommend a CT of the chest and pelvis; and an MRI of the abdomen for assessment of liver metastases. If an MRI cannot be performed, a CT chest, abdomen, and pelvis would be acceptable. Please use same imaging throughout the study.
3. History and exam include prior surgery, cancer-related and other treatment and known positivity for Hepatitis B surface antigen, Hepatitis C virus antibodies, and Human Immunodeficiency Virus antibodies 1 /-2.
4. Patient questionnaire booklets **must** be used; copies are not acceptable for this submission
5. Body weight to be measured within 72 hours prior to durvalumab administration.
6. Single 12-lead ECG after 5 min rest in supine position.

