7. Gross (dipstick) urine examination: Leukocytes, nitrite, pH, protein, glucose, ketone, urobilinogen, bilirubin, blood (hemoglobin and erythrocytes). If abnormalities are detected by dipstick, then a microscopic sediment test should also be performed. If a UTI is suspected, it can be treated.
8. Durvalumab administration over 60 minutes. Following infusion, subjects must be observed for 30 minutes post infusion for potential infusion related reactions. The number of doses administered is per dose level for each patient cohort.
9. The 2nd durvalumab dose can be done \leq 5 days prior to Y90-RE or same day as long as it is before the Y90-RE.
10. Blood biomarkers will be collected in the morning of visit. Kits are required.
11. Tissue specimens must be collected the following timepoints: pre-treatment [screening/prior to cycle 1 of Durvalumab (fresh as well as archived if available)], and post-treatment. Kits are required (banking, clinical as well as real-time send out).
12. Visit will occur 8 weeks after Y90-RE.
13. Clinical follow-up visits will be performed at least every 3 months (or as per standard physician practice) for 2 years.
14. Cohort 1- Durvalumab given at cycle 1 and cycle 2 only
15. Cohort 2- Durvalumab given at cycle 1, 2, and 4
16. Dose escalation cohort- Durvalumab given cycle 1, 2, 4 and 5
17. Dose expansion cohort- Durvalumab given cycle 1, 2, 3, 4, and 5
18. As long as the lesion is amenable to a biopsy and is done, the biopsy can be done on the Tc-99m labelled MAA eligibility mapping day to save patient a visit. Has to be prior to anti-PD1 therapy though. From a safety perspective since we need to know about the shunting to other organs prior to the Y90-RE, the mapping can be done during the screening or even prior to considerations for this study if already performed within 12 months of intended Y90-RE, it would not need to be repeated unless as per interventional radiology. Biopsy still needs to be done as noted.
19. If there is complete response of the lesion in the field of Y90-RE, tissue biopsy of the field would still be done to assess for the immune changes and an alternative tumor lesion can be biopsied for testing of the tumor itself.
20. At the time of progression, patient would be approached for a tissue biopsy and research blood sampling similar to the end of treatment visit.

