7.4.2 Definitions of Dose Limiting Toxicities (DLT)

A DLT will be defined as any Grade 3 or higher treatment-related toxicity that occurs during the DLT observation phase (8 weeks post Y90-RE), including:

- Any event resulting in a delay of cycle 2 by \geq 14 calendar days
- Any Grade 4 immune related adverse event (irAE)
- Any Grade 3 immune related AE (irAE) that does not resolve to \leq Grade 1 or to baseline with immunosuppressive therapy within 3 weeks
- Any Grade 3 colitis
- Any Grade 3 noninfectious pneumonitis irrespective of duration
- Grade 4 neutrophil count decreased lasting longer than 5 calendar days
- Grade 4 platelet count decreased
- Grade 3 platelet count decreased with hemorrhage
- Any \geq Grade 2 pneumonitis that does not resolve to \leq Grade 1 within 7 days of the initiation of maximal supportive care
- Any other Grade 3 irAE (excluding colitis or pneumonitis), that does not downgrade to Grade 2 within 7 days after onset of the event despite optimal medical management including systemic corticosteroids or does not downgrade to \leq Grade 1 or baseline within 14 days
- Liver transaminase elevation $> 8 \times$ ULN
- Total bilirubin $> 5 \times$ ULN
- AST or ALT $> 5-8 \times$ ULN with concurrent increase in total bilirubin $> 2 \times$ ULN without evidence of cholestasis or alternative explanations, e.g., viral hepatitis, disease progression in the liver, etc. (Hyll's Law). Exception: If it is present at cycle 3 but resolves at cycle 4 it is not a DLT.
- Any \geq grade 3 non-hematologic toxicity, except:
 - Grade 3 nausea or vomiting that lasts < 48 hours and resolves to \leq Grade 1 either spontaneously or with conventional medical intervention
 - Grade 3 nausea, vomiting, and diarrhea lasting < 72 hours in the absence of maximal medical therapy
 - Grade 4 vomiting and diarrhea lasting < 72 hours in the absence of maximal medical therapy
 - Grade 3 hypertension in the absence of maximal medical therapy
 - Grade 3 metabolic abnormalities (e.g. hypokalemia, hypomagnesemia, hypocalcemia, hypophosphatemia) that recover to \leq Grade 1 within 48 hours
 - \geq Grade 3 electrolyte abnormality lasting < 72 hours, is not clinically complicated, and resolves spontaneously or responds to conventional medical intervention.
 - Grade 3 or 4 elevation in serum amylase and/or lipase that are not associated with clinical or radiographic evidence of pancreatitis.
 - Grade 3 rash < 5 calendar days

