10.2.2 Reporting window

The adverse event collection window is from the first treatment (durvalumab or TheraSphere) through 30 days after the final administration (durvalumab or TheraSphere). Medical records and study records will be reviewed for up to 2 years post-embolization for radiation-induced adverse events. These will be assessed by the IDE-sponsor or delegate and captured in the electronic data capture system.

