17.2 MTD Definition and Determination

For this protocol, the patient must return to clinic for evaluation at least every **14** days +/- 5 days. Patients will be treated and observed for a minimum of **8** weeks post-Y90-RE before new patients are treated. Doses will not be escalated in any individual patient.

MTD Definition: The MTD will be defined as the highest dose level for which at most 1 out of 6 patients experience a dose-limiting toxicity (DLT). A total of 6 patients treated at the MTD will be sufficient to identify common toxicities at the MTD. For instance, those toxicities with an incidence of at least 25% will be observed with a probability of at least 82% (1-(1-0.25)⁶).

Refer to Section **7.42** for definition of dose-limiting toxicity (DLT).

MTD Determination:

This study will utilize an accelerated titration design. The dose levels to which patients will be assigned in sequential cohorts are listed in the table below.

		Immunotherapy (Durvalumab) Administrations					
		Pre-Y90 doses		Post-Y90 doses		Number of Administration of Durvalumab	
Dose level	Week -2	Week 0	Y90-Radio-embolization	Week 2	Week 4	Week 6	
					X		1
-2					X		2
-1							2
1 (start)	X	X					3
2	X	X		X			4
3	X	X		X	X		5
4	X	X		X	X	X	

In the first phase, a single patient will be treated per dose level until the first DLT is recorded. Once the first DLT is recorded, two additional patients are treated at the same dose level and the trial reverts to a standard 3+3 design in the second phase. At which time, decisions on when and how to dose escalate are described below.

Number of patients with DLT at a given dose level	Decision Rule
0 out of 3	Enter 3 patients at the next higher dose level
1 out of 3	Enter up to 3 additional patients at the same dose level. 
 • If 0 of these 3 patients experience DLT, proceed to the next dose level. • If 1 or more of these 3 patients experience DLT, then dose

	escalation is stopped, and this dose is declared the maximally administered dose. Three (3) additional patients will be entered at the next lowest dose level if only 3 patients were treated previously at that dose.
≥2 out of 3	Dose escalation will be stopped. This dose level will be declared the maximally administered dose. Three (3) additional patients will be entered at the next lowest dose level if only 3 patients were treated previously at that dose.

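### AE collection under 10.2.2 closes 30 days after the last administration; at starting level 1 that is 26 days before the 8-week DLT window ends and before two AE assessments scheduled in 4.1

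*Combined protocol and SAP*

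**What the plan says.** Section 10.2.2 sets the general rule: "The adverse event collection window is from the first treatment (durvalumab or TheraSphere) through 30 days after the final administration". Its only extension is a record review, for up to 2 years, for radiation-induced events.

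Section 7.4.2 sets the period that decides escalation: "A DLT will be defined as any Grade 3 or higher treatment-related toxicity that occurs during the DLT observation phase (8 weeks post Y90-RE". Section 17.2 agrees, requiring a minimum of 8 "weeks post-Y90-RE before new patients are treated".

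The schedule in 4.1 marks the row "Adverse event assessment" at every cycle, at the end of treatment visit and at clinical follow-up. Footnote 12 places the end of treatment visit: "Visit will occur 8 weeks after Y90-RE". Footnote 14 gives the level 1 schedule: "Cohort 1- Durvalumab given at cycle 1 and cycle 2 only". Section 7.1.2 puts Y90-RE with cycle 2, after that cycle's durvalumab dose.

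Other limits are near to 10.2.2 but not identical. Sections 10.5.3 (SAEs) and 10.5.4 (unanticipated device effects) use a 30-day period after treatment is discontinued, described as what typically happens. Section 9.1 records concomitant medications and blood products to 30 days after the final dose.

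On attribution, 10.2 exempts Grade 1 and 2 events unless they are SAEs or DLTs. Goal 2.2.1 and section 17.5.2 report treatment-related toxicity with no grade limit, and 17.5.2 defines toxicity by attribution.

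**The concern.** Safety is the primary goal, and escalation opens with a single patient at level 1. If that patient has no DLT, the trial moves up. The plan gives staff two different end dates for recording adverse events inside the window on which that decision rests.

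The events at risk are mainly non-laboratory, non-radiation events after day 30, such as late immune-related toxicity. Section 8.2 itself says durvalumab events may appear months after the last dose. Some DLT rules also need information after onset. A Grade 3 immune-related event counts if it has not resolved within 3 weeks, and one exception reads "Grade 3 hypertension in the absence of maximal medical therapy", which cannot be judged without knowing what treatment was given. Section 9.1 requires the medication record only over the same 30 days.

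Without attribution, low-grade toxicity cannot be tabulated as 17.5.2 defines it. Section 8.1 does call for a relatedness judgement, but only before a durvalumab dose. At level 1 there is no durvalumab dose after Y90-RE.

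**Working it through.** The plan states no figure to reproduce; this is calendar arithmetic with Y90-RE as day 0.

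**Inputs**
- Collection ends on the day of last administration + 30 (10.2.2).
- The DLT window ends 8 weeks after Y90-RE (7.4.2, 17.2): 8 × 7 = day 56.
- Cycles last 14 days, with cycle 2 on day 0 (4.1, 7.1.2). Cycle 3 is day 14, cycle 4 day 28, cycle 5 day 42. A further 14 days gives day 56, which matches the stated week-8 visit.
- The visit window is ±5 days (4.1).

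**Level 1**
- Last administration: Y90-RE, day 0. This holds even if the second durvalumab dose is given up to 5 days earlier, as footnote 9 allows.
- Collection ends: 0 + 30 = day 30.
- Gap: 56 − 30 = 26 days; 26/56 = 46% of the DLT window.
- AE assessments between Y90-RE and week 8: days 14, 28, 42 and 56. Two of the four fall after day 30. Cycle 5 (days 37 to 47) and the week-8 visit (days 51 to 61) do so anywhere in their visit windows. Cycle 4 (days 23 to 33) could do so if late. The 3-monthly follow-up visits come later still and are also marked for AE assessment.
- Example of an event needing follow-up: with Grade 3 immune-related onset on day 20, the 3-week criterion cannot be settled before day 20 + 21 = day 41.

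**General condition**

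A gap exists when last administration + 30 < 56, that is, when the last administration is before day 26. This includes a patient at any level who stops protocol treatment soon after Y90-RE, for example under Table 8.21.

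**Other levels, all doses on the nominal day (Table 1 in 1.4.6 and the 4.1 footnotes)**

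| Level | Last dose (day) | Collection ends (day) | Gap before day 56 |
|---|---|---|---|
| 2 | 28 | 58 | none |
| 3 | 42 | 72 | none |
| 4 | 42 | 72 | none |
| −1, −2 | 42 | 72 | none |

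The level 2 entry rests on footnote 15: "Cohort 2- Durvalumab given at cycle 1, 2, and 4". If that dose is given 5 days early (day 23), collection ends on day 53, a 3-day gap. The tables in 7.4.1 and 17.2, as they read in the text available, put the level 2 dose at week 2, which would give day 14 + 30 = day 44 and a 12-day gap. That may be a column shift from text extraction, so nothing here depends on it.

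**The case against.** The strongest reply is that more specific text already secures DLT ascertainment. Section 17.2 requires 8 weeks of observation with clinic evaluation at least every 14 days. Section 4.1 schedules examination, AE and medication review, blood counts and chemistries through week 8. Sections 10.5.1, 10.5.2 and 10.5.5 set no end date, and 7.4.1.2 asks for immediate contact when a DLT occurs. For data to be lost, staff would have to carry out a scheduled assessment and then leave the result out because of 10.2.2. This stands as mitigation, and it is why no missed DLT is asserted. It does not remove the conflict: 10.5.5 and 7.4.1.2 govern an event already recognised as a DLT, and none of these sections expressly extends 10.2.2.

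A second reply is that reach is narrow. With full dosing on nominal days only level 1 is affected: one patient if there is no DLT, and up to six in escalation. That is fair for escalation. But if level 1 became the MTD, the expansion cohort towards 18 patients would also be treated there, and early stoppers at other levels are affected too.

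Third, 10.5.3 and 10.5.4 may not conflict at all. Treatment being discontinued could mean the last dose or the end of the roughly 2-month treatment phase in 1.4.6. That ambiguity is real and is itself a reason to state one date.

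Fourth, 9.1 sets a minimum for the medical record, and 4.1 schedules medication review beyond it. This softens the medication point.

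On attribution, 17.5.1 tabulates all adverse events regardless of cause, so low-grade events are not lost. Only their classification as treatment-related may be incomplete.

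**Conclusion.** The concern holds. As written, 10.2.2 ends general AE collection on day 30 at level 1, 26 days (46%) before the DLT window closes and before two scheduled AE assessments. The same kind of gap arises for any patient whose last administration is before day 26. Levels 2 to 4 and the two lower levels have none when all doses are given on the nominal days in Table 1.

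The conclusion assumes that 10.2.2 is read literally and that Y90-RE is the last administration at level 1, as footnote 14 and 7.1.2 state. The plan gives no frequency of events by time, so no number of missed events can be estimated. The likely harm is incomplete documentation of non-laboratory, non-radiation events in the window that governs escalation.

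The attribution mismatch also holds. Treatment-related Grade 1-2 toxicity may be incomplete, chiefly after the last durvalumab dose. Both points should be corrected; neither undermines the design.

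**What to change.** - **10.2.2:** collect adverse events through the later of 8 weeks after Y90-RE or 30 days after the last administration. If Y90-RE is not given, use 30 days after the last administration. Keep the 2-year radiation review unchanged.
- **10.5.3, 10.5.4 and 9.1:** state the same end date for SAEs, device effects and the concomitant-medication record.
- **10.2:** either require attribution at all grades, or limit 2.2.1 and 17.5.2 to events that are attributed (Grade 3 or higher, SAEs, DLTs).
- **While editing:** say which adverse events are recorded at the 3-monthly follow-up visits, and check the level 2 rows in 7.4.1 and 17.2 against Table 1 in the source file.

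The window change costs almost nothing, because AE and medication reviews are already scheduled for every patient at cycles 3 to 5 and week 8. All-grade attribution adds a little work for the principal investigator and the IDE sponsor. The narrower alternative avoids that work but reduces the secondary endpoint.

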8.2 Treatment schedule modifications for durvalumab

Adverse events (both non-serious and serious) associated with durvalumab exposure may represent an immunologic etiology. These adverse events may occur shortly after the first dose or several months after the last dose of treatment. Durvalumab must be withheld for drug-related toxicities and severe or life-threatening AEs per Table 8.21 below. See Section 9.0 for supportive care guidelines, including use of corticosteroids.

Table 8.21 Dose Modification Guidelines for Drug-Related Adverse Events for Durvalumab			
CTCAE System/Organ/Class	Adverse Event	Grade	Action
Gastrointestinal disorders	Diarrhea or Colitis	2	Hold all protocol treatment until Grade 0-1. If AE does not resolve to Grade 0-1 within 2 weeks, then permanently discontinue all protocol treatment
		3, 4	Permanently discontinue all protocol treatment
Investigations	Alanine aminotransferase increased, Aspartate aminotransferase increased, and blood bilirubin increased	2	Hold all protocol treatment until Grade 0-1. If AE does not resolve to Grade 0-1 within 2 weeks, then permanently discontinue all protocol treatment
		3-4	Permanently discontinue all protocol treatment
Metabolism and nutrition disorders	Glucose intolerance (Type 1 diabetes mellitus [if new onset]) or Hyperglycemia	T1DM or 2-4	Hold all protocol treatment until clinically and metabolically stable.

Table 8.21 Dose Modification Guidelines for Drug-Related Adverse Events for Durvalumab

CTCAE System/Organ/Class	Adverse Event	Grade	Action	
Endocrine disorders	Endocrine disorders-Other, specify: Hypophysitis	2-4	Hold all protocol treatment until Grade 0-1. If AE does not resolve to Grade 0-1 within 2 weeks, then permanently discontinue all protocol treatment	
	Hypothyroidism	2-4	Therapy with durvalumab can be continued while thyroid replacement therapy is instituted	
	Hyperthyroidism	2-3	Hold all protocol treatment until Grade 0-1. If AE does not resolve to Grade 0-1 within 2 weeks, then permanently discontinue all protocol treatment	
		4	Permanently discontinue all protocol treatment	
General disorders and administration site conditions	Infusion related reaction	1, 2	Follow infusion related reaction treatment guidelines (Table 9.21). Hold all protocol treatment until Grade 0-1. If AE does not resolve to Grade 0-1 within 2 weeks, then permanently discontinue all protocol treatment	

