10.2 Determination of Reporting Requirements

Toxicity will be graded according to NCI's Common Toxicity Criteria (CTCAE v5). The principal investigator will have final responsibility for determining the attribution of toxicity as it is related to durvalumab. The IDE sponsor will have final responsibility for determining the attribution of toxicity as it is related to 90Y-TheraSpheres.

The clinical research team is responsible for collecting and recording the research data. As these results are collected, all toxicities and adverse events will be identified and reported to the principal investigator (PI). The principal investigator (PI) will determine final relationship of the event to the investigational product (ascorbate):

- Grade 1 and 2 events do not require attributions assigned.
- Grade 3 and higher adverse events require attribution assigned to durvalumab and 90Y TheraSpheres.
- All serious adverse events, regardless of severity, require attribution assigned to durvalumab and 90Y TheraSpheres.
- All dose limiting toxicities, regardless of severity, require attribution assigned to durvalumab and 90Y TheraSpheres.

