10.5.3 Serious Adverse Events

Any experience or condition meeting the definition of a serious adverse event (SAE; 21CFR312.32) occurring in a study subject from the first day of study treatment and typically continue through the 30-day follow-up period after treatment is discontinued will be captured. Investigators **must** report to the DSMC any SAE, regardless of attribution to study drug. SAEs must be reported *via* an OnCore SAE Report \leq 1 business day of learning of the event.

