15.2 Nursing Guidelines

- 15.2.1 Anti PD-L1 side effects vary greatly from those of traditional chemotherapy and can vary in severity from mild to life threatening. Instruct patients to report any side effects to the study team immediately. Side effects may be immediate or delayed up to months after discontinuation of therapy. Most side effects are reversible with prompt intervention of corticosteroids.
- 15.2.2 Diarrhea can be common and can be very severe, leading to colonic perforation. Instruct patients to report ANY increase in the number of stools and/or change in baseline, blood in the stool, abdominal pain to the study team immediately.
- 15.2.3 Rash/pruritis/dermatitis is seen. Patients should report any rash to the study team. Treat per section 8.0 and monitor for effectiveness.
- 15.2.4 Monitor LFT's closely as elevations in these levels could indicate early onset autoimmune hepatitis. Patients should also be instructed to report any jaundice, or right upper quadrant pain to the study team immediately.
- 15.2.5 Pneumonitis can be seen and may be mild (only seen on imaging) to severe. Patients should be instructed to report any SOB, dyspnea, cough, chest pain, etc. to the study team immediately. Patients reporting these symptoms should have a pulse ox checked and consider immediate imaging per the treating MD.
- 15.2.6 Endocrinopathies (including hypopituitarism, hypothyroidism, hypophysitis, and adrenal insufficiency) are a concern given the mechanism of action of this agent. Patients may present only with the vague sense of fatigue and "not feeling well". Additional symptoms may be that of nausea, sweating and decreased activity tolerance. Instruct patients to report these signs or symptoms immediately and obtain appropriate labs as ordered by MD.
- 15.2.7 Pancreatitis is possible with anti PD-L1 therapy based on mechanism of action. Instruct patients to report abdominal pain, nausea and vomiting to the study team.
- 15.2.8 Patients who are started on steroid therapy for any side effects of anti PD-L1 toxicity should be instructed to take the steroids as ordered, and not to discontinue abruptly as symptoms may return and be severe. Patients may be on steroid therapy for weeks. Instruct patients to report any increase or change in side effects with any dosage decrease as patients may need a slower taper.

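### Late immune-related toxicity can be under-captured: after its 30-day window, section 10.2.2 reviews records only for radiation-induced events, and other sections conflict with it

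*Combined protocol and SAP*

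**What the plan says.** **Collection windows.** In section 10.2.2 the general AE window runs from first treatment "through 30 days after the final administration (durvalumab or TheraSphere"). For the time after that it provides one thing: "Medical records and study records will be reviewed for up to 2 years post-embolization for radiation-induced adverse events". On who judges those events it adds: "These will be assessed by the IDE-sponsor or delegate and captured in the electronic data capture system". Section 10.5.3 covers serious events that start on the first treatment day and "typically continue through the 30-day follow-up period after treatment is discontinued will be captured". Section 10.5.4 uses the same 30-day wording for unanticipated device effects.

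**Timing of durvalumab events.** Section 8.2 says: "These adverse events may occur shortly after the first dose or several months after the last dose of treatment". Section 15.2.1 says: "Side effects may be immediate or delayed up to months after discontinuation of therapy".

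**Follow-up.** The row "Adverse event assessment" in the 4.1 schedule is marked in every column, including the 3-monthly clinical follow-up. Footnote 13 runs those visits for 2 years. Section 1.4.6 says that after the end-of-treatment visit the study does no active follow-up except for PFS and OS. Patients who progress move to survival follow-up (13.2, 13.5, 13.6), and its table in 4.2 has no AE row.

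**Attribution and analysis.** Section 10.2 states: "Grade 3 and higher adverse events require attribution assigned to durvalumab and 90Y TheraSpheres". It gives the principal investigator the final say on durvalumab and the IDE sponsor the final say on the device. Sections 17.5.1 and 17.5.2 summarise events overall, by dose level, by patient and by tumor group or site, with relatedness judged to study treatment as a whole.

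**The concern.** The protocol names a delayed risk and then sets its general collection window to close before much of that risk has passed. The late review is defined by cause, and only one of the two agents is named as the cause. An event judged purely immune-related has no stated route into the data under 10.2.2.

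Events of unclear cause are the harder case. Section 15.1 lists raised AST/ALT and radiation pneumonitis among known durvalumab toxicities. The package insert in Appendix VI lists hepatitis, pneumonitis and their radiation forms for the device, and describes a hepatitis death about 5 months after treatment that was judged possibly device-related. Under 10.2.2 a late hepatic or pulmonary event enters only if the IDE sponsor or delegate first judges it radiation-induced. The investigator responsible for durvalumab attribution is not named at that step.

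At stake are the primary goal (2.1.1, feasibility and safety of the combination) and goal 2.2.1 (its treatment-related AEs). Dose levels differ only in the number and timing of durvalumab doses, so late durvalumab toxicity bears directly on the recommended dose.

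**Working it through.** The plan gives no figure for this point, so there is none to reproduce. The check is on the length of the windows.

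**Inputs.** Y90-RE is day 0. The last administration comes from Table 1 in 1.4.6 and footnotes 14-17 of 4.1: week 0 at level 1 (Y90-RE itself is last), week 4 at level 2, week 6 at levels 3 and 4. The window is 30 days (10.2.2), the DLT period is 8 weeks or 56 days (7.4.2), and the record review is 2 years or 730 days. The half-life is about 18 days (15.1.5).

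**Formula.** Closing day = 7 × week of last administration + 30.

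| Level | Closing day | Relative to day 56 | Rest of the 730 days |
|---|---|---|---|
| 1 | 0 + 30 = 30 | 26 days before | 700 (96%) |
| 2 | 28 + 30 = 58 | 2 days after | 672 (92%) |
| 3, 4 | 42 + 30 = 72 | 16 days after | 658 (90%) |

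The dose tables are broken in the available text. If the last level 2 dose were at week 2, that window would close on day 14 + 30 = 44, which is 12 days before day 56. All rows assume dosing on schedule. A patient who stops durvalumab early has an earlier closing day.

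For 90-96% of the 2-year period, then, 10.2.2 provides for radiation-induced events only. General capture after Y90-RE also differs by level, 30 days against 72, which affects the by-dose-level tables in 17.5.1.

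**Residual drug, as context.** 0.5^(30/18) = 0.31, so about 31% of the last durvalumab dose remains 30 days after it. Five half-lives are 5 × 18 = 90 days, which section 3.1.10 counts as 13 weeks. Neither figure measures missed events.

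**How many late events could there be?** The documents give no rate, so the following is an assumption. If each of 18 patients has probability q of a late qualifying event, the expected number is 18q and the chance of at least one is 1 − (1 − q)^18:

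- q = 5%: 0.9 expected, 60% chance of at least one
- q = 10%: 1.8 expected, 85%
- q = 20%: 3.6 expected, 98%

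These are events that could occur, not events that would be lost.

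**Sections side by side.** Sections 10.2.2, 10.5.3 and 1.4.6 point to no general AE capture after 30 days. The 4.1 schedule points to about 24/3 = 8 further visits with an AE assessment. No section says which governs, or whether a non-radiation event found at such a visit is graded, attributed, entered and analysed.

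**The case against.** The strongest reply is that 10.2.2 should not be read alone. The schedule has an unrestricted AE assessment at 3-monthly visits for 2 years, with chemistry and thyroid tests. Section 10.5.3 says only that capture typically ends at 30 days. IRB reporting of serious durvalumab-related events (10.3.1) and routine capture of adverse effects (10.5.2) state no time limit. This stands: it would be wrong to say that the protocol as a whole captures only radiation-induced events after 30 days. It shows an unresolved conflict, not a settled wider rule, and it does not cover patients in survival follow-up.

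A reader might also infer that late toxicity is credited to Y90-RE by construction, or that the split between agents is biased. The documents do not support either. A late event judged purely immune-related is omitted, not assigned to Y90-RE. Grade 3+ and serious events need attribution to both agents, and the two attributions are not mutually exclusive. No planned summary splits toxicity by agent.

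Nor does level 1 lose its dose-limiting immune events after day 30. DLTs are observed to day 56 and reported within 1 business day (10.5.5), and the end-of-treatment visit at 8 weeks has an AE assessment. At level 1 the 26-day gap concerns AEs that are not DLTs, and the inconsistency between the two windows.

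Finally, patients may resume chemotherapy after the end-of-treatment visit, so a limited window for all AEs is defensible. That is a reason to restrict late capture by severity and to record later therapy. It is not a reason to restrict it to one suspected cause.

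**Conclusion.** The concern holds as under-capture. As written, 10.2.2 and 10.5.3 give no assured route for immune-related or combined toxicity that appears more than 30 days after the last dose, although 8.2 and 15.2.1 expect such events. The 4.1 schedule points the other way, and the conflict is unresolved. Late hepatic or pulmonary events of unclear cause enter under 10.2.2 only through a radiation judgement.

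The closing days of 30, 58 and 72 and the 26-day mismatch at level 1 rest on on-schedule dosing and on the level 2 dose falling at week 4. They describe the windows. How many events would be missed cannot be derived from the documents. MTD decisions rest on the 8-week DLT period and are not put in doubt by this point. What is exposed is the completeness of the late safety record of the combination. It should be corrected, and the correction is small.

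**What to change.** 1. In 10.2.2, widen the existing 2-year record review to all Grade 3+ or serious events possibly related to either agent, naming immune-related events, with attribution to both agents as in 10.2.
2. Make the general AE window run at least to the end of the 8-week DLT period at every dose level.
3. Bring 10.5.3, 10.5.4, 1.4.6 and 4.1-4.2 into line with this. State that qualifying events found at the 3-monthly visits are recorded and analysed, and that record review continues for patients in survival follow-up.
4. Record the start date of any new anticancer therapy, and tabulate late events before and after it separately.

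The cost is wording changes and a few extra event records in 18 patients. The 2-year review and the visits are already planned, and treatment does not change. The downside is that some late events will be confounded by later therapy. The recorded start date makes this visible but does not remove it.
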